### **13.2 Randomization/Stratification**

Participants will be registered on Day 1 after they have satisfied the inclusion/exclusion criteria. All participants will have been assigned a unique subject number [e.g., 7-character subject identification]. Twelve patients will be randomized to each arm (24 total; dolcanatide or placebo, where participants will be treated once daily for a period of 7 days).

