### 13.4 Primary Objective, Endpoint(s), Analysis Plan

**Primary Endpoint:** To a direct comparison of the pharmacological effect on cGMP levels for dolcanatide arm vs. placebo, where this effect is defined below:

**Pharmacological Effect on cGMP levels:** Arithmetic difference in mean cGMP levels before and after 7 days of dolcanatide from subject biopsies. This represents the increase in cGMP stimulated by 7 days dolcanatide in an individual subject. The mean cGMP value will be calculated based on 8 biopsies from the rectum assessed at each time point.

With a sample size of 12 per arm, we'd have 80% power to detect a significantly increased Pharmacological Effect of the continuous cGMP results for dolcanatide vs. placebo, assuming a 1-sided significance level of 5%. The study would be powered to detect an effect size of 1 (i.e. [difference in means]/SD = 1). Prior data from one of the active doses for the MAY2012-00-01 study found a difference in means of around 4 for the PD effect (5 vs. 1), with an SD of around 4 as well. This would be an example of an effect size of 1 (4/4). Given this prior data, we believe an effect size of 1 is achievable. We'll also report the 2-sided 95% confidence intervals as well for final results. If the cGMP values are not normally distributed, a transformation to a variable with a normal distribution will be performed. See the detailed calculations below:

Let  $x_{zij}$  = baseline cGMP level for person  $i$  in randomization group  $z$  with replicate  $j$ .

$$x_{zimean} = \sum_j x_{zij} / 8 = \text{mean baseline level}$$

Let  $y_{zij}$  = day 7 cGMP level for person  $i$  in randomization group  $z$  and replicate  $j$ .

$$y_{zimean} = \sum_j y_{zij} / 8 = \text{mean baseline level}$$

Let  $i$  index person and  $z = 0, 1$  index group.

$$\text{Let } d_{zi} = (y_{zimean} - x_{zimean}) = \text{effect in person } i \text{ in group } z.$$

$$d_{zmean} = \sum_i d_{zi} / 12 = \text{mean effect over all persons in group } z$$

$$\text{var}_z = \sum_j (d_{zi} - d_{zmean})^2 / 11$$

$$\text{var}_{zmean} = \text{var}_z / 12 = \text{variance of mean effect in group } z$$

$$\text{dif} = d_{1mean} - d_{0mean}$$

$$\text{vardif} = \text{var}_{1mean} + \text{var}_{0mean}$$

$$\text{sedif} = \text{sqrt}[\text{vardif}].$$

The final result is dif with two-sided 95% confidence interval, dif-1.96 sedif, dif+1.96 sedif.

The sample size per randomization group is:

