$N = (z_\alpha + z_{\text{power}})^2 \text{ vardif} / \text{dif}^2$ , where  $z_\alpha$  and  $z_{\text{power}}$  are z-statistics for type I error and power.

The anticipated values are

$$\text{var}_{1mean} = 4^2 \text{ and } \text{var}_{0mean} = 4^2, \text{ and } \text{dif} = 4;$$

Substituting into the formula, gives sample size for one arm as

$$N = (z_\alpha + z_{\text{power}})^2 * (32 / 16) = ((z_\alpha + z_{\text{power}})^2) * 2$$

It is important to keep type error at .05 for the analysis. Let us say it is one-sided. Suppose the power is .8 Then  $N = ((1.645 + .84)^2) * 2 = 12.35$ , which rounds to 12 per arm.

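### Section 13.4: the primary-analysis formulas sum the arm variance over biopsies instead of persons and fix the divisors at 12 and 11, although fewer than 12 per arm may be evaluable

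*Combined protocol and SAP*

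**What the plan says.** Section 13.4 defines i as the person, j as the replicate biopsy and z as the arm. Each participant's change d_zi is the Day 7 biopsy mean minus the baseline biopsy mean, each being a sum over j divided by 8. The arm-level steps are:

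- d_zmean = Σ_i d_zi / 12, described as the "mean effect over all persons in group" z;
- var_z = Σ_j (d_zi − d_zmean)² / 11;
- var_zmean = var_z / 12, described as the "variance of mean effect in group" z;
- dif = d_1mean − d_0mean, with sedif = √(var_1mean + var_0mean) and a 95% interval of dif ± 1.96 sedif.

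The sample-size step then puts var_1mean + var_0mean into N = (z_α + z_power)² vardif / dif². After "The anticipated values are" it sets var_1mean and var_0mean each to 4² and dif to 4. The Day 7 biopsy mean carries the label of the baseline mean.

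Other sections bear on the counts. Section 13.2 states: "Twelve patients will be randomized to each arm". Section 13.8 limits the primary analysis to eligible participants who started intervention and have both sets of biopsies. Section 13.6 expects no drop-outs. Section 12.4, however, has the DSMB consulted if 25% or more miss the second sigmoidoscopy, Section 5.6 provides for permanent discontinuation for some toxicities, and Section 8.3 only encourages post-intervention procedures after early stopping. Section 10.2 has five of the eight biopsies frozen and two of those five evaluated for cGMP, whereas Sections 7.2 and 7.4 have all samples frozen for cGMP.

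**The concern.** These lines are the prespecified rule for the primary estimate and its interval, and no other formulas are given.

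The variance line sums over an index that its summand does not carry, so taken literally it is not an arm variance.

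The constants 12 and 11 are the planned size and the planned size minus one. If an arm has fewer evaluable participants, dividing their sum by 12 pulls that arm's mean toward zero. The arm's variance of the mean then also uses a sample size that was not achieved. The estimate is biased and the interval is too narrow.

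The divisor 8 raises the same issue at participant level if fewer than eight biopsies are assayed.

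**Working it through.** **Inputs.** All are from Section 13.4 unless noted. Type I error is one-sided ("assuming a 1-sided significance level of 5" percent). Power: "With a sample size of 12 per arm, we'd have 80% power". Effect size: "The study would be powered to detect an effect size of 1". Prior data "found a difference in means of around 4 for the PD effect (5 vs. 1), with an SD of around 4 as well". The numbers evaluable used below are assumptions, because the plan gives none other than 12 per arm.

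**The plan's own figure.** With SD = 4 as the between-person SD of the change and a difference of 4:

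N = (1.645 + 0.84)² × (16 + 16)/16 = 6.175 × 2 = 12.35 per arm.

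This reproduces the plan. The 4² used is the per-person variance. A true variance of a mean of 12 would be 16/12 per arm and would give N = 1.03, which the plan did not do. The symbol is wrong; the number is not.

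**Variance index.** Because d_zi has no j, the literal sum over eight replicates is 8(d_zi − d_zmean)²/11 for one unspecified person. With SD 4 and 12 persons, the expected squared deviation is 16 × 11/12 = 14.67. The expression therefore averages 8 × 14.67/11 = 10.67 (simulated median 4.9), against a true variance of 16.

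**Fixed divisors, estimate.** Read the sum as over persons and assume mean changes of 5 (active) and 1 (placebo). With n₁ and n₀ evaluable, the expected difference is 5n₁/12 − n₀/12.

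| Evaluable, active / placebo | Expected difference (true value 4) | Simulated coverage of dif ± 1.96 sedif |
|---|---|---|
| 12 / 12 | 4.00 | 93.7% |
| 11 / 11 | 3.67 | 93.0% |
| 10 / 10 | 3.33 | 91.3% |
| 10 / 12 | 3.17 | 90.4% |

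The right comparison for coverage is about 93.5%, not 95%. With correct divisors, the 1.96 multiplier (in place of t = 2.07 on 22 degrees of freedom) already gives 93.7% at 12/12 and 93.5% at 10/12.

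**Fixed divisors, standard error at 10 active / 12 placebo.** Take the active arm's ten changes to have mean 5 and variance 16.

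- Arm mean as written: 50/12 = 4.17.
- Sum of squares about 4.17: 9 × 16 + 10 × (5 − 4.17)² = 150.9.
- var_1mean as written: 150.9/11/12 = 1.143. Correct value: 16/10 = 1.6.
- Placebo, either way: 16/12 = 1.333.
- sedif as written: √(1.143 + 1.333) = 1.57. Correct value: √(1.6 + 1.333) = 1.71.
- Ratio: 1.57/1.71 = 0.92, about 8% too small.

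**Biopsy divisor.** If two biopsies were assayed and their sum divided by 8, each participant mean would be 2/8 = one quarter of its true value, and a difference of 4 would be reported as 1. If the number assayed were the same throughout, sedif would shrink by the same factor, so the ratio of estimate to standard error would not change.

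**The case against.** The strongest reply is that the intent is plain and a competent analyst would carry it out. The divisor 11 = 12 − 1 and the description of the arm mean as taken over all persons show that a sum over persons was meant. The literal sum could hardly be programmed unnoticed, and i for j is a one-character difference in a subscript, worth checking against the typeset original. The constants state the planned size: Section 13.3 expects 24 evaluable, Section 13.6 expects no losses, and at 12 per arm the divisors are exact. Dividing ten values by 12 would contradict the plan's own description of the result as a mean.

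This stands as to intent and likelihood. It does not make the written rule correct. The evaluability definition allows fewer than 12, and other sections provide for early stopping and missed second sigmoidoscopies.

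It may also be said that the bias runs against a false positive. That depends on the arm: with 12 active and 10 placebo, the expected difference is 5 − 10/12 = 4.17, above 4.

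A reader might go further and infer that the sample-size step is wrong, or that the trial is badly underpowered, because 4² stands under the symbol for the variance of a mean. The documents do not support this. Taking that symbol at its word implies an SD of √(16 × 12) = 13.9, whereas the same section states an SD of about 4 and an effect size of 1.

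**Conclusion.** The point holds in a limited form. As written, the variance formula has the wrong index and is not a valid arm variance, although the intended formula is recoverable. The fixed divisors are wrong whenever an arm does not have exactly 12 evaluable participants.

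The harm is nil at 12 per arm. It is modest at 11 per arm, where the estimate is 8% low. At 10 active and 12 placebo the estimate is 21% low and coverage is about three points below what correct divisors would give. These sizes rest on normally distributed changes with means 5 and 1 and SD 4, and on assumed evaluable counts.

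The divisor 8 cannot be settled from the documents, because Section 10.2 and Section 13.4 imply different numbers of assayed biopsies.

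The variance symbols in the sample-size step and the Day 7 label are labelling errors only. Rounding 12.35 down to 12 and the use of 1.96 are separate matters on which this point does not rest.

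**What to change.** In Section 13.4:

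1. Let n_z be the number of evaluable participants in arm z with both biopsies. Write d_zmean = Σ_i d_zi / n_z, var_z = Σ_i (d_zi − d_zmean)² / (n_z − 1) and var_zmean = var_z / n_z, with i running from 1 to n_z.
2. Divide each biopsy mean by the number of biopsies actually assayed for that participant and visit. Reconcile the stated 8 with the two in Section 10.2, and carry the result into the PD-response formulas in Section 13.5, which also use 8.
3. In the sample-size step, write the inputs and vardif with var_1 and var_0 (each 4²) in place of var_1mean and var_0mean. N = 12.35 is unchanged.
4. Relabel the Day 7 biopsy mean.

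Items 1, 3 and 4 are text corrections with no operational cost. Item 2 needs a decision on how many biopsies are assayed; the formula change itself costs nothing.

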## 2.5 Endpoints

The overall objective of this study is to evaluate the effect of dolcanatide on GCC-related signaling in the colorectum. Tissue samples from the rectum will be collected by flexible sigmoidoscopy before and after administration of dolcanatide or placebo. The primary PD endpoint for this trial is a statistically significant elevation of cGMP after 7 days of dolcanatide administration. A secondary endpoint is to assess the safety and tolerability of dolcanatide at the assigned dose among healthy adult volunteers. Another secondary endpoint is to determine whether or not dolcanatide can induce a PD effect on cGMP in rectal mucosa biopsies when administered as a single daily dose for 7 days without a concurrent colonoscopy bowel preparation.

In the previous study, translational endpoints were focused on examining the impact of dolcanatide on cGMP downstream targets (VASP phosphorylation) and function (regulation of proliferation by Ki67) in intestinal mucosa. Here, rectal mucosa biopsy specimens will be collected and stored to enable future assessment of these translational endpoints to confirm the cGMP PD endpoint, if required.

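### Section 13.4 pairs 1.96 with variances estimated from 12 people per arm, so its 95% interval covers about 93.7%; the primary test is unnamed and the stated 80% power is 78.9%

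*Combined protocol and SAP*

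**What the plan says.** Section 13.4 defines each participant's effect, `d_zi`, as mean cGMP on Day 7 minus mean cGMP at baseline. For each arm it takes the sample variance of `d_zi` (divisor 11) and divides it by 12. It adds the two results without pooling and takes the square root to get `sedif`. It then states: "The final result is dif with two-sided 95% confidence interval, dif-1.96 sedif, dif+1.96 sedif".

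Earlier in the section, the plan claims "80% power to detect a significantly increased Pharmacological Effect of the continuous cGMP results for dolcanatide vs. placebo" with 12 per arm, one-sided 5%, and an effect size of 1 (difference about 4, SD about 4). There the interval is something the team will "also report the 2-sided 95% confidence intervals as well for final results".

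The two quantiles in the sample-size formula "are z-statistics for type I error and power", set at 1.645 and 0.84. The result is 12.35, "which rounds to 12 per arm". The same paragraph says: "It is important to keep type error at .05 for the analysis. Let us say it is one-sided". Section 2.5 adds: "The primary PD endpoint for this trial is a statistically significant elevation of cGMP after 7 days of dolcanatide administration".

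Section 13.4 gives no test, reference distribution, degrees of freedom or critical value for the primary comparison.

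**The concern.** The quantiles 1.96 and 1.645 are exact only when the variances are known. Here they are estimated from the trial, on 11 degrees of freedom per arm and at most 22 in total. The interval is therefore too narrow for its label. A test using 1.645 would exceed the 0.05 error that the section itself calls important.

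Because no test is named, the choice between a normal and a t cut-off stays open until the data are seen. With SD 4 in both arms, `sedif` is 4 × √(2/12) = 1.633. A normal cut-off then needs a difference of 1.645 × 1.633 = 2.69, and a t cut-off on 22 df needs 1.717 × 1.633 = 2.80. A result between these two values would change verdict with the choice.

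The power shortfall has a different cause: rounding 12.35 down.

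**Working it through.** **Inputs (Section 13.4).** One-sided error 0.05; difference 4; SD 4 in each arm; 12 per arm; variance divisor 11; interval multiplier 1.96; planning quantiles 1.645 and 0.84. Section 13.6 expects no drop-outs, so all 24 are taken as evaluable. Data are assumed normal, after the plan's transformation if needed.

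**1. The plan's own figure.** N = (1.645 + 0.84)² × 32/16 = 2 × 2.485² = 12.35 per arm. This reproduces the plan. Reaching 80% by this formula requires rounding up to 13.

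**2. Power at 12 by the plan's formula.** The standardised difference is 4/1.633 = √6 = 2.449. Power = Φ(2.449 − 1.645) = Φ(0.804) = 78.9%. At 13 per arm it is 81.7%.

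**3. Coverage and error, equal SDs.** With equal arms and equal SDs, dif/`sedif` under no effect is taken as t on 22 df.
- Coverage of ±1.96 `sedif`: 1 − 2 × P(T > 1.96) = 1 − 2 × 0.0314 = 93.7%.
- One-sided error of a 1.645 cut-off: P(T > 1.645) = 5.7%.

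**4. Power of a t-test that holds 5%.** Noncentral t, noncentrality √6, cut-off 1.717 on 22 df: 76.7%. The Welch version, by simulation, has 76.5%.

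**5. Unequal SDs.** The plan gives no arm-specific SDs, so a 2:1 ratio is an assumption, with the average variance held at 16. Welch degrees of freedom for variances in ratio 4:1: (4 + 1)² / (16/11 + 1/11) = 275/17 = 16.2, for which the 97.5% quantile is 2.12.

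Results (simulation of 2,000,000 trials per case with the plan's unpooled `sedif`; it agrees with the exact values for equal SDs):

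| | Equal SDs | SD ratio 2:1 |
|---|---|---|
| Coverage, ±1.96 `sedif` | 93.7% | 93.3% |
| One-sided error, 1.645 cut-off | 5.7% | about 6.0% |
| Welch interval coverage | 95.1% | 95.0% |
| Welch one-sided error | 4.9% | 5.0% |
| Welch power | 76.5% | about 76% |
| Multiplier in place of 1.96 | 2.07 | 2.12 |
| Mean width relative to the 1.96 interval | 1.06 | 1.08 |

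With SD 4 in both arms, the half-width goes from 1.96 × 1.633 = 3.20 to 2.074 × 1.633 = 3.39.

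**6. Notation.** The sample-size formula enters 4² as `var_1mean` and `var_0mean`, which the section defines as the arm variance divided by 12. The per-person variance is clearly meant, and N is unaffected.

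**The case against.** The strongest reply is that only the interval is certainly wrong, and only slightly.

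- **The 5.7% is conditional.** In Section 13.4, 1.645 appears only in the sample-size formula, where normal quantiles are a normal planning shortcut. If the team runs a t-test, the error is 5%. This stands. The firm statement is that the test is unnamed, and 5.7% is what follows if 1.645 is used.
- **The power gap is immaterial.** The difference and SD are given only as about 4. By the plan's formula, an SD of 4.4 gives 72% power and an SD of 3.6 gives 86%, so a gap of 1 to 4 points lies well inside the planning uncertainty. This also stands. It is a reason to restate the figure, not to enlarge the trial.
- **About 77% depends on a test the plan does not name.** True. With a 1.645 cut-off and estimated variances, power is 78.8%; about 77% is the price of holding 5%. Welch rather than pooled t is my choice because it matches the unpooled `sedif`. With equal SDs the two differ by 0.2 points.
- **The interval is only descriptive.** The plan does introduce it as an extra report, but later calls it the final result. Under either reading, an interval labelled 95% should have about that coverage.

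**Conclusion.** The concern holds. The prescribed interval covers about 93.7% with equal SDs and somewhat less with unequal SDs (93.3% at 2:1). Both figures assume normal data. This defect follows directly from the written formula.

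The error rate is open because no test is named: 5% with a t cut-off, about 5.7% to 6.0% with 1.645. The 80% power claim is slightly high: 78.9% by the plan's own formula, and about 77% for a t-test holding 5%, at effect size 1 with all 24 evaluable.

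One clarification belongs with this. Sections 2.5 and 13.4 lean towards the one-sided test as the deciding analysis, but no sentence says so. The effects are small, and the interval and a 1.645 cut-off both err in the anti-conservative direction. They should be corrected before analysis.

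**What to change.** In Section 13.4:

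1. Name a one-sided 5% Welch two-sample t-test on `d_zi` as the primary test.
2. Replace 1.96 with the Welch t quantile, using degrees of freedom computed from the data (about 2.07 if the SDs are equal, about 2.12 at a 2:1 ratio).
3. Restate power as about 77% at effect size 1 with 12 evaluable per arm.
4. Add one sentence saying that the one-sided test decides and the two-sided 95% interval is descriptive.
5. In the sample-size formula, write `var_1` and `var_0` in place of `var_1mean` and `var_0mean`.

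The cost is wording only. The interval becomes about 6% wider with equal SDs and about 8% wider at 2:1, and the stated power is about 3 points lower. No participants are added.

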### 13.5 Secondary Objectives, Endpoints, Analysis Plans

The following secondary endpoints will be assessed between treatment arms. The analysis of secondary endpoints will include a Bonferroni correction for multiple comparisons.

#### **Estimate the Pharmacodynamic (PD) Response rate across all patients and compare between arms:**

Each participant will be assessed for PD response. The calculation is based on the standardized difference in means for the pharmacological effect on cGMP levels at the participant level, as shown in the following mathematical formulas, where a subject with a  $z \geq 1.645$  will be considered a PD responder. A participant with a  $z < 1.645$  will be considered a non-responder. If the cGMP values are not normally distributed, a transformation to a variable with a normal distribution will be performed. The PD response rate will be compared between the 2 arms using a standard Chi-square or Fisher's exact test. See the detailed calculations below for how the analysis will be done for calculating whether or not a subject is a PD responder:

Let  $i$  index persons and  $z$  index randomization group. For each time (baseline and final) there are 8 biopsies or replicates.

$$\text{Let } x_{zij} = \text{baseline cGMP level for person } i \text{ in randomization group } z \text{ with replicate } j.$$

$$x_{z\text{imean}} = \sum_j x_{zij} / 8 = \text{mean baseline level}$$

$$v_{zi} = \sum_j (x_{zij} - x_{z\text{imean}})^2 / 7 = \text{variance of baseline level for one replicate for person } i \text{ in group } z$$

$$v_{z\text{imean}} = v_{zi} / 8 = \text{variance of mean of baseline replicates for person } i \text{ in group } z$$

Let  $y_{zij}$  = day 7 cGMP level for person  $i$  in randomization group  $z$  and replicate  $j$ .

$$y_{z\text{imean}} = \sum_j y_{zij} / 8 = \text{mean baseline level}$$

$$w_{zi} = \sum_j (y_{zij} - y_{z\text{imean}})^2 / 7 = \text{variance of final level for one replicate for person } i \text{ in group } z$$

$$w_{z\text{imean}} = w_{zi} / 8 = \text{variance of mean of final replicates for person } i \text{ in group } z$$

$$\text{Let } z\text{stat}_{zi} = (y_{z\text{imean}} - x_{z\text{imean}}) / \text{Sqrt}[v_{z\text{imean}} + w_{z\text{imean}}]$$

Define  $PD_{zi}$  an indicator of a statistically significant increase (at one-sided alpha of .05) in mean cGMP from baseline to final result for person  $i$  in group  $z$ .

Let  $PD_{zi} = 1$  if  $z\text{stat}_{zi} \geq 1.645$ , and 0 otherwise.

**To confirm the safety and tolerability of dolcanatide:** Summary statistics and frequency tables will be used to describe the data in an exploratory fashion. All adverse events will be summarized by treatment arm and compared between arms using the Fisher's Exact test. All eligible participants initiating study intervention will be considered evaluable for this endpoint.

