### **Screening 2**

Participants will be limited to clear liquids until noon and then fast, with free access to water, until the flexible sigmoidoscopy at about 3:00 p.m. Participants will be given PEG enemas about 1.5 hours prior to sigmoidoscopy. Up to 3 enemas may be administered until evacuation is clear. PEG enemas are being used because they have been demonstrated to be optimum for preserving epithelial cell integrity for biopsy and subsequent analyses.

Eight mucosal biopsies will be obtained from 8 discrete areas in the rectum (each separated by no less than 0.5 cm in any direction). In addition, all biopsies will be obtained from areas no less than 0.5 cm above the dentate line. All samples will be flash-frozen in liquid nitrogen and stored at  $-80^{\circ}\text{C}$  for analysis of cGMP.

Following the sigmoidoscopy, a meal will be provided. Medically stable participants can be discharged at the discretion of the investigator, or participants may be kept overnight for prolonged observation for safety. Specifically, participants who are experiencing pain, bleeding, respiratory distress, fever, or other clinical manifestations that might indicate that a complication occurred during the procedures will be observed overnight or until the symptoms resolve.

Incidentally noted endoscopy findings that are felt to be potentially clinically relevant, in the opinion of the endoscopist, will be biopsied for histologic review. Specimens from any incidentally noted findings obtained by sigmoidoscopy will be fixed in formalin (10%) and sent to the Pathology Department at Thomas Jefferson University for diagnostic assessment. The investigator will review findings with study participants and discuss their continuation in the study. Participants will be referred to primary care physicians or gastroenterologists for further diagnosis and therapy, as appropriate, according to institutional standards of good clinical practice.

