#### **7.4 Evaluation at Completion of Study Intervention**

##### **Day 7**

Participants will arrive at the CRU in a fasted state in the morning. Adverse events (AE), concomitant medications, and vital signs will be assessed. Blood will be drawn for safety testing (albumin, total bilirubin, calcium, bicarbonate, chloride, creatinine, glucose, alkaline phosphatase, potassium, total protein, sodium, AST/SGOT, ALT/SGPT, BUN, CBC with differential, PTT and PT/INR), urinalysis, urine drug screen, and a brief physical exam will be performed. An oral dose of dolcanatide or placebo will be administered under direct supervision of the CRU staff at approximately 07:00 a.m. Participants will be limited to clear liquids until 12:00 p.m. and remain fasting thereafter until the scheduled sigmoidoscopy, which will take place approximately 8 hours after the dolcanatide /placebo dose time. Participants will be given the first of a maximum of 3 enemas beginning at approximately 1:30 p.m.

Eight mucosal biopsies will be obtained from 8 discrete areas in the rectum (each separated by no less than 0.5 cm in any direction). In addition, all biopsies will be obtained from areas no less than 0.5 cm above the dentate line. All samples will be flash-frozen in liquid nitrogen and stored at -80°C for analysis of cGMP. Any abnormalities identified during the procedure will be handled and followed according to standards of usual clinical practice. Following the sigmoidoscopy the participants will be discharged to the CRU after recovery. A light meal will be provided. Medically stable participants can be discharged at the discretion of the investigator, or participants may be kept overnight or prolonged observation for safety. Specifically, participants who are experiencing pain, bleeding, respiratory distress, fever, or other clinical manifestations that might indicate that a complication occurred during the procedures will be observed overnight or until the symptoms resolve.

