### **10.2 Collection and Handling Procedures**

- Eight mucosa biopsies will be collected from the rectum (at or just above the inferior valve of Houston) pre-intervention and post-intervention (Day 7, after administration of dolcanatide or placebo for 7 days).
- Five biopsies will be flash-frozen in liquid nitrogen individually in a screw cap vial and provided a sample-specific ID. Among the 5 biopsies, 2 of them will be evaluated for cGMP concentration. Frozen tissues will be transferred and stored at -80°C in [name] laboratory. In addition, 3 biopsies will be flattened immediately and fixed in 10% formalin within 2 min of collection in pre-labeled cassettes with tracking information provided, for future Ki67 immunohistochemistry analysis, if necessary.
- After formalin fixation overnight, samples will be transferred to 70% ethanol and sent to the Pathology Department for routine tissue processing. Processed tissue will be transferred to [name] laboratory for biomarker studies.
- All specimens from the each biopsy will be put into pre-labeled containers separated for analysis.
- Containers will be labeled with study number, registration number, date/time of collection, anatomical location and biopsy number. For example, 000-D7-Rec-1.
- Specimen manifest will be sent by email to the Biospecimens Resource Manager at the time of shipment.

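### The PD-responder cutoff of 1.645 is labelled one-sided alpha .05, but its nominal size is 6.1% with 8 replicates per visit and would be 12.1% with the 2 per visit of section 10.2

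*Combined protocol and SAP*

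**What the plan says.** Section 13.5 defines PD response participant by participant. The change in mean cGMP from baseline to day 7 is divided by a standard error built from that participant's own replicates: a sample variance at each visit with divisor 7, described for baseline as the "variance of baseline level for one replicate for person" concerned, then divided by 8, with the two visits added. A participant at or above 1.645 is a responder, and the indicator is described as "an indicator of a statistically significant increase (at one-sided alpha of .05) in mean cGMP from baseline to final result". There is no t reference and no small-sample correction. Response rates are then compared between arms by chi-square or Fisher's exact test. For the secondary endpoints, "The analysis of secondary endpoints will include a Bonferroni correction for multiple comparisons".

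The documents disagree on how many replicates there will be:

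- Section 13.5: "For each time (baseline and final) there are 8 biopsies or replicates".
- Section 13.4: "The mean cGMP value will be calculated based on 8 biopsies from the rectum assessed at each time point".
- Section 7.4 (Day 7): "All samples will be flash-frozen in liquid nitrogen and stored at -80°C for analysis of cGMP". Section 7.2 (Screening 2) has the same freezing instruction.
- Section 10.2: five biopsies are frozen and three go to formalin. "Among the 5 biopsies, 2 of them will be evaluated for cGMP concentration".

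**The concern.** The cutoff 1.645 has a 5% upper tail only when the standard error is known. Here it is estimated from a handful of biopsies in one person, so the reference distribution has heavier tails and unchanged participants cross the line more often than 5% of the time. How much more often depends on the replicate count, which is the item the documents leave unsettled.

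The denominator also holds only the scatter among biopsies taken at the same visit. If a person's rectal cGMP differs between two visits for reasons unrelated to drug, that variation enters the numerator but not the denominator, and the background responder rate rises further.

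Comparing PD response rates is the first secondary objective (section 1.2), and section 13.5 also asks for the rate to be estimated across all patients. A reader told that each responder is significant at .05 will expect about 5% false responders in each arm, and the rule does not deliver that.

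**Working it through.** **Inputs.** The cutoff 1.645, the stated one-sided .05, the replicate number n = 8 per visit and the divisors 7 and 8 come from section 13.5. The alternative n = 2 comes from section 10.2. If all the frozen biopsies of section 10.2 were assayed, n would be 5; no section says this will be done. There are 12 participants per arm (section 13.1). Normality is the plan's own condition, since it transforms otherwise. Equal replicate variance at the two visits is an assumption, relaxed below.

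**The plan's figure.** 1 − Φ(1.645) = 0.04998. The stated .05 is reproduced, but only as a known-variance or large-sample result.

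**The rule as written.** The statistic is (ȳ − x̄) / √(v/n + w/n), with v and w sample variances. With equal n this denominator is the pooled two-sample t denominator, so with no true change, normal replicates and equal variances the statistic is exactly t on 2(n − 1) degrees of freedom.

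| Replicates per visit | df | P(t ≥ 1.645) | Expected among 12 unchanged | 5% critical value |
|---|---|---|---|---|
| 8 | 14 | 0.0611 | 0.73 | 1.761 |
| 5 | 8 | 0.0693 | 0.83 | 1.860 |
| 2 | 2 | 0.1209 | 1.45 | 2.920 |

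At a true 5% the expected number is 12 × 0.05 = 0.60. Simulation with 1,000,000 null draws per setting gave 0.0612 for n = 8 and 0.1206 for n = 2. The chance of two or more responders among 12 unchanged participants is 12% at a true 5%, 16% at 6.1% and 44% at 12.1% (binomial).

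**Unequal variances.** The documents give no ratio of day 7 to baseline replicate SD. At assumed ratios of 2, 3 and 10, simulation gives 6.5%, 6.7% and 7.1% for n = 8, and 13.3%, 14.5% and 16.8% for n = 2. The ceiling is t on n − 1 df: P(t₇ ≥ 1.645) = 7.2% and P(t₁ ≥ 1.645) = 17.4%.

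**Visit-to-visit variation.** The documents give no figure, so its effect cannot be computed from them. As an illustration only, with n = 8 and an assumed visit SD of 0.25 times the replicate SD, simulation gives about 10% at cutoff 1.645 and about 9% at 1.761. At 0.5 times it gives about 18% and 16%.

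**Effect of a t cutoff on the between-arm comparison.** Assume a true shift of 2 standard errors in the active arm and none on placebo. Responder rates come from the noncentral t; power is for a two-sided Fisher test with 12 per arm. The .025 column assumes that the Bonferroni correction covers two secondary endpoints; section 13.5 does not state the number.

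| Replicates | Cutoff | Active rate | Placebo rate | Power, alpha .05 | Power, alpha .025 |
|---|---|---|---|---|---|
| 8+8 | 1.645 | 64% | 6.1% | 82% | 68% |
| 8+8 | 1.761 | 60% | 5.0% | 79% | 63% |
| 2+2 | 1.645 | 67% | 12.1% | 74% | 57% |
| 2+2 | 2.920 | 38% | 5.0% | 33% | 17% |

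The 8+8 and 2+2 rows do not describe the same absolute shift, because the standard error at 2+2 is √(8/2) = 2 times larger. A shift of 2 standard errors at 8+8 is 1 standard error at 2+2, where power at alpha .05 is about 15% with cutoff 1.645 and 2% with 2.920.

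**The case against.** The strongest reply is that nothing in the plan depends on the 5%. The stated comparison is between arms. There is no one-sample test against 5% and no go/no-go threshold, and the concurrent placebo arm already supplies an empirical background. The same rule is applied in both arms, so the Fisher comparison remains valid. On the rule as written, with 8 replicates, the excess is 1.1 percentage points, or 0.13 of a participant in 12, and a normal cutoff at 14 df is a common approximation. The 12.1% belongs to a design in which the printed divisors could not be used, and the 8-versus-2 conflict also reaches the primary endpoint, so it is a wider problem than this one. Finally, if visit-to-visit variation is material, the choice between z and t is the smaller error, and printing 6.1% would replace one model-dependent label with another.

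Most of this stands, and it limits the severity. It does not remove the error. The text makes an explicit inferential claim at a stated alpha, and that claim is wrong for every replicate count the documents support. The 12.1% is conditional, but on an instruction in section 10.2 that currently stands. The point about visit-to-visit variation is a reason to describe the rule as a within-visit criterion whichever cutoff is kept.

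**Conclusion.** The concern holds as a low-severity labelling error. The rule does not have one-sided alpha .05. Its nominal size is 6.1% with 8+8 replicates and would be 12.1% with 2+2, assuming independent normal replicates, equal variances at the two visits and no true change. Unequal variances can raise these to at most 7.2% and 17.4%. Visit-to-visit variation would raise them further, by an amount the documents do not allow to be computed. What is affected is the reading of each arm's responder rate. The between-arm type I error and the primary endpoint are not affected by the cutoff.

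**What to change.** First reconcile section 10.2 with sections 7.2, 7.4, 13.4 and 13.5 on how many biopsies per visit are assayed for cGMP, and make the divisors match that number. Then choose one of two courses:

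- **(a)** Keep 1.645 as a prespecified threshold and replace the alpha statement with the nominal size for the settled count (6.1% for 8+8, 6.9% for 5+5, 12.1% for 2+2), with its assumptions. This is one line of wording and changes no result.
- **(b)** Replace 1.645 with the matching t critical value (1.761, 1.860 or 2.920). This lowers responder rates in both arms and, for moderate effects, lowers power. At the assumed shift of 2 standard errors the loss at alpha .05 is about 3 points at 8+8 (82% to 79%) and about 41 points at 2+2 (74% to 33%). At 3 standard errors and 8+8 there is essentially no loss (99.8% with either cutoff).

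At 2+2, course (a) is clearly cheaper. Under either course, call the indicator a within-visit-variance criterion, because neither supplies the missing visit-to-visit variance, and say that the placebo responder rate is the empirical background.
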